8.2 Clinical Laboratory Assessments (Hematology, Serum Chemistry, and Urinalysis)

Clinical laboratory evaluations of hematology, serum chemistry, and urinalysis will be performed. Results and change from baseline will be summarized by treatment using descriptive statistics for numeric parameters and using counts and percentages for categorical parameters, where baseline is defined as the last value collected before the Day 1 dose in each treatment

period. Values reported with a “<” or “>” sign will be converted to numeric values and summarized.

All clinical laboratory data will be presented in data listings in chronological order by date for unscheduled or repeated values.

8.3 Vital Signs and Anthropometrics

Average blood pressure and heart rate and anthropometrics of body weight will be summarized using descriptive statistics for measurements obtained at baseline and each postdose visit and changes from baseline at each visit, by treatment, where baseline is defined as the average of the values obtained during the two pre-treatment visits in each period. Differences in the change from baseline between the treatments will be compared using a paired t-test or Wilcoxon-signed rank test depending on the distribution of the data.

All vital sign and anthropometrics data will be presented in a data listing, and data collected in duplicate will be averaged and both the individual and mean values will be presented in the data listing.

9 OTHER ANALYSES

The data presented in this section will be presented using the safety population.

9.1 Prior and Concomitant Medications

Medications will be classified according to the World Health Organization Drug dictionary (March 2019 Version) and presented in a data listing by Anatomical Therapeutic Chemical Class Level 3 and preferred drug name. Medications with an end date occurring before the first dose date/time, will be classified as prior medications. A concomitant medication will be defined as any medication taken during the study, from the time after the first dose of study drug through the last completed visit. Medications with missing dates will be assigned as prior medications unless they are indicated as occurring during the study.

Medications will be provided in a data listing by subject.

9.2 Treatment Compliance

Subjects will be instructed to take two capsules of study drug twice per day with meals during each treatment period. The number of planned capsules during each treatment period will be calculated as the number of days during the treatment period multiplied by 4 capsules/d. If a subject's treatment period spans 28 days, for example, the number of planned capsules will be 112. Study compliance (%) for each treatment period will be calculated as the number of capsules consumed divided by the number of planned capsules multiplied by 100. Overall compliance for the treatment period and number of days during the treatment period (unadjusted and adjusted for compliance) will be summarized by treatment using descriptive statistics. Compliance-adjusted days during the treatment period will be computed as the number of days during the treatment period multiplied by percent compliance for the treatment period divided by 100. The number and percentage of subjects with an overall compliance $\leq 80\%$ and $>80\%$ will also be presented by treatment. Compliance at the Day 22 visit and for the overall treatment period and the number of days during the treatment period (unadjusted and adjusted for compliance) will be provided for each treatment in a data listing by subject.

9.3 Other Ancillary Data

The 12-Lead ECG assessments, MEDFICTS total score, and urine pregnancy test results will be provided in data listings. Data collected in duplicate or triplicate will be averaged and both the individual and mean values will be presented in the data listings, if applicable.

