#### 5. Study Design and Procedures

This is an open-label, randomized, crossover study with a visit to initiate a 4-week diet lead-in period at day -28 (visit 1), up to 3 screening visits on days -14, -7 and -3 (visits 2, 3, and 3b), a randomization visit on day 1 of treatment period 1 (visit 4), two visits at the end of each treatment period (days 22 and 29; visits 5 and 6 in treatment period 1 and visits 9 and 10 in treatment period 2, and two visits after a 28-day washout period on days -7 and 1 (visits 7 and 8) to establish baseline for treatment period 2. The window to complete all screening procedures will not exceed 42 days with a minimum of 48 h between visits. A window of  $\pm 2$  days will be allowed for visits on day 22 (visits 5 and 9); the window for visits on day 29 (visits 6 and 10) will be minus 2 days only, i.e., days 27, 28 or 29. The washout period between treatments (between visits 6 and 7) should be a total of at least 28 days, but not more than 35 days.

At visit 1 (day -28), after subjects have provided informed consent, medical history information will be collected and the Meats, Eggs, Dairy, Fried foods, In baked goods, Convenience foods, Table fats, Snacks (MEDFICTS) dietary assessment questionnaire will be completed. Subjects who score  $<40$  may proceed directly to visit 2 procedures. Subjects who score  $>40$  will complete clinic visit procedures including measurements of height, body weight, resting heart rate and blood pressure, waist circumference, evaluation of inclusion/exclusion criteria and concomitant medication/supplement use (Appendix 1) and calculation of BMI. Blood pressure measurements will be taken three times, each 1 min apart after the subject has been resting quietly for 5 min. The average of the three measurements will determine eligibility for the study. Body mass index (BMI) will be calculated. Fasting (at least 9 hours, water only) blood samples will be collected for measurement of TG, total-C and HDL-C. Non-HDL-C will be calculated as total-C minus HDL-C; LDL-C and VLDL-C will be calculated using the Hopkins/Martin method. Subjects will receive instructions on the TLC diet (Appendix 3). Subjects must follow the TLC diet for the next 14 days prior to visit 2 (day -14) and the full 28 days prior to the first treatment period (visit 4, day 1). Subjects will be scheduled for visit 2 (day -14) and will receive written study instructions (Appendix 6).

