### **9.2.4 hs-CRP Confounder Checklist**

The hs-CRP Confounder Checklist (Appendix 5) will assess non-study-related factors that may confound the evaluation of the hs-CRP response and will be administered on the same visits when blood levels of hs-CRP are measured. This includes screening visit 3 (day -7), treatment 1 visits 4, 5 and 6 (days 1, 22 and 29), treatment 2 visits 8, 9 and 10 (days 1, 22 and 29) and washout visit 7 (day -7).

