## Appendix 5: hs-CRP Confounder Checklist

1. Has the subject experienced any infections within the last 7 days (with or without the use of analgesics or anti-inflammatory drugs)?
 
If yes, please explain: _____
	
Yes
	
No

2. Has the subject experienced joint pain within the last 7 days (with or without the use of analgesics or anti-inflammatory drugs)?
 
If yes, please explain: _____
	
Yes
	
No

3. Has the subject experienced any soft tissue injury within the last 7 days (with or without the use of analgesics or anti-inflammatory drugs)?
 
If yes, please explain: _____
	
Yes
	
No

4. Has the subject consumed any alcoholic beverages within the last 7 days?
 
If yes, please indicate how many: _____
	
Yes
	
No

5. Has the subject participated in vigorous exercise within the last 7 days?
 
If yes, please explain: _____
	
Yes
	
No

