hs-CRP confounder checklist			X		X	X	X	X	X	X	X
Archive samples ^g					X		X		X		X
Urinalysis		X					X				X
Urine pregnancy test ^h		X			X				X		
Physical examination			X								
12-lead ECG			X				X				X
TLC diet instruction/reinforce ⁱ	X	X	X	X	X	X	X	X	X	X	
MEDFICTS questionnaire ^j	X	X			X		X	X	X		X
Provide/review study instructions	X	X	X	X	X	X	X	X	X	X	X
Randomization					X						
Start washout period ^k							X				
Dose study product + TLC bar ^l					X				X		
Dispense study product					X	X			X	X	
Collect SP/assess compliance						X	X			X	X
Fasting Omega-3 fatty acids ^m					X	X	X		X	X	X
Fasting lipids ⁿ	X	X	X	X	X	X	X	X	X	X	X
Fasting apolipoproteins ^o					X		X		X		X
Fasting PCSK9					X		X		X		X
Treatment-emergent AEs ^p					X	X	X	X	X	X	X

Abbreviations: AE, adverse event; ECG, electrocardiogram; HbA1C, hemoglobin A1c; HIPAA, Health Insurance Portability and Accountability Act; hs-CRP, high-sensitivity C-reactive protein; MEDFICTS, Meats, Eggs, Dairy, Fried Foods, In baked goods, Convenience foods, Table fats, Snacks; PCSK9, proprotein convertase subtilisin kexin type 9; SP, study product; TLC, Therapeutic Lifestyle Changes; TSH, thyroid stimulating hormone; WO, washout.

- ^a To adjust for subject scheduling, the allowable window to complete all screening procedures will not exceed 42 days with a minimum of 48 hours between all visits. If the subject is already following a Therapeutic Lifestyle Changes (TLC) diet at visit 1 supported by the Meats, Eggs, Dairy, Fried Foods, In baked goods, Convenience foods, Table fats, Snacks (MEDFICTS) score, they can proceed directly to visit 2 procedures. A TLC diet lead-in of 14 days prior to the qualification visit (visit 2, Day -14) will be required. A window of ±2 days will be allowed for visits on Day 22 (visits 5 and 9); the window for visits on Day 29 (visit 6 and 10) will be minus 2 days only, i.e., Days 27, 28 or 29. The washout period between treatments (between visits 6 and 7) should be a total of at least 28 days, but not more than 35 days.
- ^b Health Insurance Portability and Accountability Act (HIPAA) authorization for disclosure of protected health information. Signed document authorizes the use and disclosure of the subject's Protected Health Information by the Investigator and by those persons who need that information for the purposes of the study. If a subject does not require a dietary lead-in based on MEDFICTS score, the first two visits should be combined.

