4 GENERAL STATISTICAL CONSIDERATIONS

All analyses described in this plan are considered *a priori* analyses in that they have been defined before locking the database. All unplanned statistical analyses, if any, designed after the SAP is finalized, will be considered *post hoc* analyses and will be applied as exploratory methodology. All *post hoc* analyses will be identified as such in the clinical study report in the changes to the planned analyses section, as appropriate. Instances where the details of the SAP differ from the protocol, the SAP will be used as the source of the procedures for data analyses.

All statistical tests will be tested at $\alpha = 0.05$, 2-sided significance level, unless otherwise stated. Descriptive statistics for continuous variables will include number of subjects/observations (N, n), mean, median, standard deviation (SD), minimum, maximum, and first [25th percentile] and third [75th percentile] quartiles (Q1, Q3), unless otherwise noted. Confidence intervals will be presented where appropriate. Descriptive statistics for categorical variables will consist of frequency and percentage.

Summary statistics will be presented as follows: N and n will be presented without any decimals, minimum and maximum to the same precision as the reported values, means and median to 1 more level of precision than the reported values, and SD to 2 more levels of precision than the reported values, or as otherwise decided upon by the study team. Data listings will be sorted by subject number.

All statistical analyses will be conducted using SAS[®] Version 9.4 (SAS Institute Inc., Cary, NC) or later using procedures appropriate for the particular analysis.

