7 PHARMACODYNAMIC ANALYSES

7.1 Pharmacodynamic Data

The pharmacodynamic analyses will be performed on available data from subjects in the PD population and repeated for the ITT and PP populations.

The PD outcome variables will be summarized using descriptive statistics by treatment at baseline, each postdose visit, and end of treatment (if the average) for the results, change from baseline, and percent change from baseline values. The PD outcomes will be presented in a data listing by parameter for each subject with data. Individual and mean values will be presented, as applicable.

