All AEs captured in the database will be presented in by-subject data listings and identified as a non-TEAE, on-treatment TEAE, or off-treatment TEAE. However, only TEAEs will be summarized.

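### Does leaving the hs-CRP confounder checklist out of the SAP's listings and analyses weaken the hs-CRP result?

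*SAP*

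**What the plan says.** Protocol section 9.2.4 gives the purpose of the checklist: it "will assess non-study-related factors that may confound the evaluation of the hs-CRP response". It is scheduled at visits 3 to 10, which are the eight visits at which Protocol section 9.1.7 has hs-CRP drawn. Appendix 5 contains five yes/no items with a 7-day look-back: infection, joint pain, soft tissue injury, alcohol and vigorous exercise.

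In the SAP, the row "hs-CRP confounder checklist" appears in Table 1 (section 2.3) and nowhere else. The ancillary listings in section 9.3 read: "The 12-Lead ECG assessments, MEDFICTS total score, and urine pregnancy test results will be provided in data listings". Section 7.2 analyses hs-CRP with the same log-scale mixed model as triglycerides and allows a rank transformation if the residuals are far from normal. Under section 1.2, baseline and end of treatment are each the average of two draws. On later additions, section 4 states: "All unplanned statistical analyses, if any, designed after the SAP is finalized, will be considered" post hoc, and they must be identified as such in the clinical study report.

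**The concern.** A trial that collects an instrument at every draw of a named secondary endpoint, and says the purpose is to interpret that endpoint, would normally say what it will do with the answers. This SAP does not. The gap also looks accidental. Section 6.5 states outright that nicotine use will not be listed, and section 9.3 remembers the diet questionnaire and the pregnancy tests, but neither mentions the checklist.

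If the hs-CRP results look odd, someone will turn to the checklist. The treatment is open-label and there are five items to choose from. A choice of items made after seeing the values could be steered, and an exclusion or sensitivity analysis designed then would be post hoc. At stake is the interpretation of hs-CRP, which is one of the secondary outcomes. Triglycerides do not depend on it.

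**Working it through.** **1. Is the omission real?** Yes. The checklist accompanies 8 of 8 hs-CRP draws. A search of the SAP's screening listings (6.6), pharmacodynamic listings (7.1), model (7.2), ancillary listings (9.3) and changes from the protocol (9.4) finds no listing, count, model term, exclusion rule or sensitivity analysis that names it. The documents do not contradict each other, because the protocol promises no checklist-based analysis.

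**2. What will the reader of the report see anyway?**
- Individual hs-CRP values: "The PD outcomes will be presented in a data listing by parameter for each subject with data" (SAP 7.1).
- Adverse events: "All AEs captured in the database will be presented in by-subject data listings" (SAP 8.1). Protocol section 12.3 opens with a broad definition that does not require treatment, so an untreated infection or injury can qualify. The bullets that follow are narrower, so coverage is partial.
- Events before visit 4: medical history, listed with onset and resolution dates (SAP 6.4).
- Drug-treated episodes: the medication listing (SAP 9.1).

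Infection and soft tissue injury are therefore largely visible. Alcohol and exercise are not, but both are largely permitted by the protocol, so a Yes there may be routine.

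**3. Bias or noise?** Events unrelated to the products strike either treatment in either period. Randomised sequence and the period term deal with imbalance in expectation. What remains is extra scatter, which the two-draw averages, the log model and the rank fallback already reduce.

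**4. Would dropping flagged draws reduce the scatter?** Let σ be the within-subject SD of one draw on the log scale, and suppose an event raises one of the two draws by δ. Treat the average as taken on the log scale (an approximation, since the SAP averages raw values). The expected squared error is
- both draws kept: σ²/2 + δ²/4;
- flagged draw dropped: σ².

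Dropping helps only if δ²/4 > σ²/2, that is δ > √2·σ. The documents give no σ. With an assumed σ = 0.45, the threshold is 1.414 × 0.45 = 0.636, and e^0.636 = 1.89-fold. A 1.5-fold rise is then better left in and a 3-fold rise better taken out. The checklist has no severity threshold to separate the two. A flag with no real effect always costs precision, because the variance goes from σ²/2 to σ².

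**5. How many subjects would be lost?** A subject loses an average when both of its draws are flagged. One event can flag both if the look-backs overlap. Visit 5 may fall on days 20 to 24, and for visit 6 "the window for visits on day 29 (visits 6 and 10) will be minus 2 days only, i.e., days 27, 28 or 29". The gap is therefore 3 to 9 days and the overlap, max(0, 7 − gap)/7, runs from 0 to 4/7 = 57%. At the nominal days 22 and 29 it is 0. Visits 3 and 4 need be only 48 hours apart, giving 5/7 = 71%.

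With flag rate f per draw, carry-over probability c (set equal to the overlap, or to an intermediate 0.3) and four averages per subject, the loss is 1 − [1 − f(c + (1 − c)f)]⁴. Both f and c are assumptions.

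| f | c = 0 | c = 0.3 | c = 0.57 |
|---|---|---|---|
| 5% | 1.0% | 6.5% | 11.3% |
| 10% | 3.9% | 14.0% | 22.4% |

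For example, f = 10% and c = 0.57 gives 0.1 × (0.57 + 0.043) = 0.0613, and 1 − 0.9387⁴ = 22.4%. Putting c = 0.71 on the period 1 baseline alone gives 0.1 × (0.71 + 0.029) = 0.0739, and 1 − 0.9261 × 0.9387³ = 23.4%. Against the 85 evaluable subjects planned, the range is about 1 to 20.

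**6. Does the plan already allow a filter?** No. SAP section 5.2 averages every value provided and accepts a single value only when one alone is reported. A flagged value is still a reported value, so a filter would need an explicit exception to that rule.

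**The case for a change.** The best argument for acting is that a rule costs little and removes temptation. One listing, one table of Yes counts and one supportive model, limited to the two acute items (infection and soft tissue injury) and fixed before database lock, would leave the main analysis unchanged and stop anyone choosing items after seeing the data.

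Part of this stands. The checklist was evidently overlooked, and the other listings replace it only in part. But the listing and the counts would change no estimate, interval or conclusion. Protocol section 14.3 requires protocol information to be entered in the case report form, so the answers can be listed on request without amending the plan.

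The supportive model has real drawbacks. Six of the eight checklists (visits 5 to 10) are completed after randomisation, by self-report, in an open-label trial. Removing values on such answers conditions on something treatment or expectation could influence, so it could bring bias into a comparison that has none. Selective use later is already contained, because SAP section 4 makes any late exclusion or sensitivity analysis post hoc and requires it to be labelled. The one softer spot is the open covariate sentence in SAP section 7.2, under which a checklist covariate might be argued to be planned. That sentence names no checklist item, and it cannot produce an exclusion or a filtered analysis.

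**Conclusion.** No change to the plan follows. The SAP leaves an hs-CRP questionnaire unlisted and unused, which is a housekeeping gap that analysts can fill with a listing if anyone asks for one. The all-values hs-CRP analysis remains valid, and the expected effect of unrelated events is noise in one secondary endpoint.

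A filtered analysis is a trade-off with no demonstrable gain. It helps only when flagged draws are raised by more than √2 within-subject SDs, and under assumed flag rates of 5% to 10% it would cost between 1.0% and about 23% of subjects a complete average. This rests on two assumptions: that the checklist events are unrelated to the products, as the protocol describes them, and that flag rates are of the order used here. The documents supply neither a flag rate nor an hs-CRP SD. If the events were in fact related to treatment, removing those draws would be harder still to defend.

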9.4 Changes From the Protocol

Changes made to the planned analyses in the protocol while all study staff were still blinded to the treatment sequences are summarized below.

- The baseline for Period 1 PD parameters is changed to use the last 2 values, rather than all 3 values if there is an additional screening visit. This change is to avoid bias between the calculation of baseline for both periods.
- The PP dataset and analysis will include all subjects who are included in the PD population for whom compliance for both study periods was at least 80%, and for whom

no clinically important protocol violations or deviations occurred during the trial.

- The PD dataset will include subjects for whom the estimation of PD parameters will be possible for 2 periods. PD parameters will not be estimated from measurements obtained more than three days (72 hours) after the most recent dose of study drug.
- The ITT dataset will include all subjects who are randomized to a treatment sequence.
- All secondary and exploratory outcomes are changed to percent change from baseline, rather than change from baseline as previously designated for hsCRP and all omega-3 fatty acid endpoints.
- Changes in plasma phospholipid levels of omega-3 fatty acids from baseline to Days 22 and 29 of each treatment period will be analyzed both as a concentration and a percentage of total fatty acids. These analyses will be exploratory.
- Exploratory analyses of lipids, apolipoproteins, PCSK9, hs-CRP, and plasma, plasma phospholipid, and erythrocyte membrane levels of omega-3 fatty acids will be performed using data from the first treatment period only.
- Changes in vital signs and anthropometrics will be assessed as safety outcomes.

